#### Safety

The frequencies of serious adverse events which included death, graft loss, infections (including CMV and BK infection), post-transplant diabetes mellitus, neurologic events, transaminitis and acute FK-induced nephrotoxicity will be recorded. Acute FK toxicity was defined as  $\geq 15\%$  increase in serum creatinine with a return to baseline after FK dose reduction and after exclusion of other causes of renal transplant graft function deterioration.

#### FK measurement and genotyping

FK trough level will be determined in whole blood using liquid chromatography and tandem mass spectrometry (LC-MS/MS) method.

Two venous blood samples (3 mL each) for CYP3A5 genotyping will be obtained from all study participants. The subjects' blood samples will be de-identified and sent to the molecular laboratory in Tan Tock Seng Hospital, Singapore, which is offering CYP3A5 genotyping as a clinical service. Briefly, the genomic DNA is extracted from ethylenediaminetetraacetic acid anticoagulated whole blood samples using a QIAamp DNA mini kit (Qiagen, Hilden,

Germany), according to the manufacturer's protocol. Real-time polymerase chain reaction (RT-PCR) is then performed with a 7900 Real-Time PCR System. RT-PCR consisted of a denaturation step at 95°C for 10 minutes, then 50 cycles of 15 seconds at 92°C and 1 minute 30 seconds at 69°C. CYP3A5 6986A>G (rs776746) allelic discrimination is undertaken with a Custom TaqMan® SNP Genotyping Assay and VIC and FAM reporter dyes. No phenotyping will be done for CYP3A5. Once the blood sample has been genotyped, it will be destroyed as agreed upon by the molecular laboratory at Tan Tock Seng Hospital. The genotyping results will then be re-identified by the PI or co-investigators. The genotyping result will not be communicated to the subjects.

The blood sample will be destroyed immediately after sample analysis.

#### Clinical assessment

Demographic and baseline data included the age, gender, race, weight and height of the recipient, cold ischemia time, the flow panel-reactive antibody value before transplantation and at its peak, the CMV serostatus of the donor and recipient. Laboratory data — including hemoglobin level, white-cell and platelet counts, FK trough level, liver function panel, serum creatinine level and estimated glomerular filtration rate — are measured at baseline, days 0 through 7, 14±3, 30±3, 60±3 and 90±3.

#### Withdrawal from study

Subjects may withdraw voluntarily from participation in the study at any time.

Possible reasons for discontinuation from the study include

- Switched out from tacrolimus to other immunosuppressants
- No longer on triple immunosuppressants either due to intolerance or infection-related complications
- Graft failure or death

If voluntary withdrawal occurs, the subject will be asked to continue scheduled evaluations, complete an end of study evaluation, and be given appropriate care under medical supervision until the symptoms of any adverse event resolve or the subject's condition becomes stable.

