### **4.3. Inclusion Criteria**

To be eligible for inclusion into the study, the subject should meet the following criteria:

- On follow up at SGH between the ages of 21 and 75 years old who had received or are

- scheduled to receive a living donor renal transplant between January 2016 to January 2023
- Has to receive tacrolimus (FK) (Prograf®; Astellas Pharma, Singapore), mycophenolic acid (MPA) (Cellcept®; Roche, Basel, Switzerland or Myfortic®; Novartis Pharma AG, Basel, Switzerland) and prednisolone as triple immunosuppressive drug maintenance regimen

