#### Endpoints

The primary endpoint of the study is the proportion of patients within the desired FK trough level at first steady state e.g. morning of day 3 after five unaltered FK doses and the proportion of patients within target FK levels on day 7 post initiation of FK. The FK trough level is defined as the whole blood concentration 12 h  $\pm$  15 min after the previous dose taken the night before at 8pm. Thereafter, the clinicians can change the FK dose based on the measured FK

level and/or the clinical situation of the individual patient according to routine transplant immunosuppression protocol. For the genotyping arm, the pre-specified FK target range will be 10 – 15 ng/mL in the first 1 week after transplantation and subsequently adjusted based on routine transplant immunosuppression protocol.

Secondary pharmacokinetic endpoints include

- Proportion of patients within target FK levels on day 7 post renal transplant
- Average FK level during the first 1 weeks after transplantation
- Average daily dose of FK the first 90 days post transplantation [days 3, 7, 14±3, 30±3, 60±3, 90±3 days post transplantation]
- Average concentration-to-dose ratio of FK during the first 90 days post transplantation [days 3, 7, 14±3, 30±3, 60±3, 90±3 days post transplantation]
- Time to reach the first target FK range
- Number of FK dose adjustments required to reach the target FK level
- Number of markedly sub-therapeutic FK level (defined as <4 ng/mL) and markedly supra-therapeutic FK level (defined as > 20 ng/mL)

Secondary clinical endpoints include

- Incidence of biopsy-proven acute rejection (BPAR), with histologic characteristics described accordingly to the Banff criteria [Banff 1997 scoring system with 2007 modifications] and/or clinically presumed acute rejection
- Incidence of graft loss (defined as failure to discontinue dialysis or if patient undergoes graft nephrectomy)
- Renal function at month 3 after transplantation. Estimated GFR (eGFR) will be calculated using CKDEPI equation. [Time Frame: at day 7, 14, 30±3, 60±3 and 90±3 days after transplantation ]

All patients will be followed for at least 3 months after transplantation, or until graft loss occurs (defined as death with a functioning transplant, return to dialysis or re-transplantation), whichever occurs earlier.

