## **8.2. Statistical and Analytical Plans**

For the analysis of efficacy, the intention-to-treat analysis will be used, which will include all patients who were treated with at least one dose of FK. Categorical variables are reported using frequency and percentages while continuous variables are expressed as medians with ranges. A chi-square statistic will be used to evaluate the null hypothesis of no difference between the standard dose group and genotype based group within the FK target range on day 3 after transplantation. Continuous data will be compared using the Mann-Whitney U test. The time to reach target FK range will be estimated with Kaplan-Meier survival analysis and compared between the groups using log-rank test. To estimate the overall effect of CYP3A5 genotype on the outcome variables of FK daily dose, FK trough concentration and dose-adjusted FK level (a measure of apparent oral clearance), a mixed between-within subjects analysis of variance will be used. This analysis will also be used to estimate the overall effect of dosing approach on renal function. All data are analysed using R Core Team (2017). A p-value < 0.05 is considered statistically significant.

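### Patients who switch off tacrolimus or leave triple therapy may be discontinued from the study itself, with no stated follow-up, which conflicts with the 3-month follow-up rule and weakens the intention-to-treat analysis of clinical outcomes

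*Protocol*

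**What the plan says.** The Withdrawal from study part of Protocol section 5 opens its list with "Possible reasons for discontinuation from the study include". The three entries are "Switched out from tacrolimus to other immunosuppressants", "No longer on triple immunosuppressants either due to intolerance or infection-related complications" and "Graft failure or death". The level named is the study, not the study regimen. On what happens afterwards it says only "If voluntary withdrawal occurs, the subject will be asked to continue scheduled evaluations", and it is silent on evaluations after a discontinuation that is not voluntary.

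Three other places bear on this:

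- **Section 5, Endpoints:** "All patients will be followed for at least 3 months after transplantation, or until graft loss occurs". Graft loss is defined there to include death with a working graft. A change of drug is not given as a reason to stop following a patient.
- **Section 8.2:** for efficacy, "the intention-to-treat analysis will be used", with the set defined by receipt of one or more tacrolimus doses.
- **Section 4.3:** subjects in both cohorts must receive tacrolimus, mycophenolic acid and prednisolone "as triple immunosuppressive drug maintenance regimen". No time point is attached to this requirement.

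**The concern.** Stopping a regimen and leaving a study are different events, and the protocol merges them. Intolerance, infection and tacrolimus toxicity may be related to exposure, and exposure is what the intervention changes. Section 3 itself names renal impairment as a risk of high levels and rejection as a risk of low ones. Patients who leave may therefore differ in prognosis from those who stay, and the share who leave may differ between the arms.

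What is at stake is the second half of the hypothesis in section 2, that earlier target attainment leads to better clinical outcome. That rests on rejection, graft loss and renal function to month 3, together with the safety events. If collection stops at the switch, the later part of this information is missing selectively. The study is open-label, and a discontinuation that is possible rather than required leaves the decision to judgement.

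**Working it through.** The protocol states no rate of switching, rejection or dropout, so there is no figure of its own to reproduce. The check is a comparison of the passages, followed by an illustration on assumed values.

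**Passages side by side.** Take a patient switched off tacrolimus on day 20.

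1. Endpoints: followed to at least 3 months, since no graft loss has occurred.
2. Withdrawal from study: may be discontinued from the study, with no instruction to continue evaluations because the withdrawal is not voluntary.
3. Section 8.2: remains in the intention-to-treat set, having had at least one tacrolimus dose.

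Items 1 and 2 conflict for this patient. Items 2 and 3 can coexist, but the patient is then in the analysis set with no outcome data after the switch.

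**Which endpoints are exposed.**

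- Day 3 and day 7 target attainment: before most switches, so little affected.
- Tacrolimus level, dose and concentration-to-dose ratio after a switch: these do not exist, so the rule does not cause their absence.
- Graft failure and death: graft loss is a secondary endpoint, both are recorded under Safety, and the Endpoints rule also ends follow-up there. The event is kept.
- Rejection, eGFR (day 14 to day 90) and safety events after a switch: exposed.

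Section 8.2 compares renal function between dosing approaches with a mixed between-within analysis of variance. In its classical form this needs complete repeated measures, so a patient without later visits could drop out of it altogether.

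**Illustration (all inputs assumed).** Let p be the 90-day risk in patients who stay on triple therapy, d the share who leave, and RR the relative risk in leavers.

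- True risk = (1 − d)·p + d·p·RR
- Stayers only = p
- Leavers kept in the denominator, all their events missed = (1 − d)·p

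With p = 10%:

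| d | RR | True | Stayers only | Leavers event-free |
|---|---|---|---|---|
| 5% | 1 | 10.0% | 10% | 9.5% |
| 5% | 3 | 11.0% | 10% | 9.5% |
| 10% | 2 | 11.0% | 10% | 9.0% |
| 20% | 1 | 10.0% | 10% | 8.0% |
| 20% | 3 | 14.0% | 10% | 8.0% |

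Over d = 5% to 20% and RR = 1 to 3, the understatement is 0 to 4.0 points for stayers only and 0.5 to 6.0 points for leavers counted as event-free.

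For a between-arm contrast, assume RR = 3 with 5% leaving in one arm and 15% in the other:

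- True: 0.95 × 0.10 + 0.05 × 0.30 = 11%, against 0.85 × 0.10 + 0.15 × 0.30 = 13%.
- Leavers kept, all their events missed: 0.95 × 0.10 = 9.5%, against 0.85 × 0.10 = 8.5%. The order of the arms reverses.
- Stayers only: 10% against 10%. This requires deleting leavers from the denominator, which section 8.2 does not allow.

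These are upper ends for the given inputs, because a rejection before or at the switch would still be recorded.

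**The case against.** The strongest reply is that the protocol never says such patients are removed. The reasons are only possible ones. Events up to the switch can be recorded under Endpoints and Safety. Section 7.2 has data retrieved to 3 months after transplantation with no exception for switchers, and patients stay under standard-of-care follow-up (section 6.3). Handling of missing data is commonly left to a statistical analysis plan, and this is a pilot with no power claim. Leaving triple therapy can also mean stopping mycophenolate or prednisolone, which need not reflect the starting tacrolimus dose.

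Much of this stands, and it rules out several stronger readings:

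- A reader might infer that the rule deletes the outcomes of patients with toxicity or infection. It does not: data already collected stay, including the event that triggered the switch.
- A reader might add graft failure and death to what is lost. Both are recorded, and both end follow-up under the Endpoints rule too.
- A reader might say that intention-to-treat is contradicted. Membership of that set is fixed by one tacrolimus dose and survives discontinuation. What suffers is the completeness of the data behind it.
- A reader might infer that controls who switched are never enrolled. The triple-regimen criterion has the same wording for both cohorts and does not require controls to be on the regimen still. It leaves the time point open, so uneven application is possible but not stated.

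The reply does not remove the conflict over follow-up. Who is followed and what is collected is protocol content, and an analysis plan cannot recover data that were not collected.

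**Conclusion.** The point holds as a conflict over follow-up and a risk of selective missing data. The protocol lets patients who switch off tacrolimus or leave triple therapy be discontinued from the study and states continued evaluation only after voluntary withdrawal, whereas Endpoints has all patients followed for at least 3 months or until graft loss. Intention-to-treat in section 8.2 is undermined, not contradicted.

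The consequence falls on rejection, eGFR and safety outcomes after a switch, and so on the clinical-outcome half of the hypothesis. No size can be drawn from the documents. The figures above rest wholly on assumed risks and leaving rates, and the bias between arms depends on leaving being related to both arm and prognosis, which is plausible but not shown. The point should be corrected, but it does not threaten the main pharmacokinetic result.

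**What to change.** Reconcile Withdrawal from study, Endpoints and section 8.2:

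1. Separate discontinuation of the study regimen from withdrawal from the study, and place the switch off tacrolimus and the departure from triple therapy under the former.
2. State that rejection, graft loss, death, eGFR and adverse events are collected to day 90 for every patient given at least one tacrolimus dose, unless consent for data collection is withdrawn, and are analysed in the patient's original group.
3. End only the tacrolimus pharmacokinetic series at the switch.
4. Apply the same rule to the historical controls, and give the section 4.3 criterion a time point by reading it as the regimen started at transplant in both cohorts.

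This changes data collection and wording, not treatment. The cost is a protocol amendment: data are already to be retrieved to 3 months (section 7.2) and patients are in routine follow-up at the same hospital.

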#### Research Data Confidentiality

Data will be retrieved from the time of preparation for renal transplantation to 3 months after renal transplantation. Any individually-identifiable data obtained during the course of this study will be stored and used only for the purposes of this study. These data will not be used for future research.

The study team will store all research data in a password protected computer in the investigators' office with key access. Only the principal investigator and co-investigators have access to the research data and the research data will be saved in a password protected file.

The research data will be retained in a secured storage facility for a minimum of 7 years after completion of research study or date of publication of the research using the research data, whichever is later. These documents will be retained by the Principal Investigator in a secure storage facility, accessible for inspection and copying by authorized authorities.

## **6. SAFETY MEASUREMENTS**

### **6.1. Definitions**

Serious adverse event (SAE) in relation to human biomedical research, means any untoward medical occurrence as a result of any human biomedical research which:

- results in or contributes to death
- is life-threatening
- requires in-patient hospitalisation or prolongation of existing hospitalisation
- results in or contributes to persistent or significant disability/incapacity or
- results in or contributes to a congenital anomaly/birth defect
- results in such other events as may be prescribed

Adverse event (AE) in relation to human biomedical research means any untoward medical occurrence as a result of any human biomedical research which is NOT serious. Adverse event can be any unfavourable and unintended sign (including an abnormal laboratory finding), symptom, or disease possibly/ probably/ definitely associated with the participant in the human biomedical research.

### **6.2. Collecting, Recording and Reporting of Serious Adverse Events (SAEs) to CIRB**

Only related SAEs (definitely/ probably/ possibly) will be reported to CIRB. Related means there is a reasonable possibility that the event may have been caused by participation in the research. Please refer to the CIRB website for more information on Reporting Requirement and Timeline for Serious Adverse Events.

The investigator is responsible for informing CIRB after first knowledge that the case qualifies for reporting. Follow-up information will be actively sought and submitted as it becomes available.

Related AEs will not be reported to CIRB. However, the investigator is responsible to keep record of such AEs cases at the Study Site File.

### **6.3. Safety Monitoring Plan**

The data and safety monitoring will be performed by the Principal Investigator (PI) and a team of Co-Investigators. The patient will be reviewed daily when hospitalized and will then be followed up at outpatient as per current standard of care. Data will be reviewed by the PI on a three-monthly basis and it will be stored in an encrypted device. Study will be stopped if more than 25% of the patients in the genotyping arm have a tacrolimus trough of < 3 ng/mL or > 20 ng/mL on day 3

As an additional safety precaution, the tacrolimus drug levels achieved with current protocol and the starting dose of tacrolimus will be reviewed after every 10 participants recruited. The starting dose will not deviate from the dosage recommended in the drug insert.

## **6.4. Complaint Handling**

Complaints from research participants will be addressed by the principal investigators or co-investigators to ensure that suitable resolutions can be identified to protect the rights and welfare of research participants, while ensuring appropriate privacy and confidentiality protections are in place throughout the process. Research participants may also contact the SingHealth Centralised Institutional Review Board for any feedback about the research study.

## **7. DATA ANALYSIS**

### **7.1. Data Quality Assurance**

Data will be collected by investigators who are trained in the field of renal transplantation to ensure that the data is accurate, complete and reliable. For subjects in the prospective arm, the data will also be collected real-time to ensure that the information is utilized efficiently.

Data will be reviewed by the PI on a three-monthly basis. After data collection, 10% of cases will be randomly selected for review to ensure accurate and complete data collection, with an acceptable error rate of <5%

### **7.2. Data Entry and Storage**

Data will be retrieved from the time of preparation for renal transplantation to 3 months after renal transplantation and stored electronically in a password protected file. Any individually-identifiable data obtained during the course of this study will be stored and used only for the purposes of this study. These data will not be used for future research.

The study team will store all research data in a password protected computer in the investigators' office with key access. Only the principal investigator and co-investigators have access to the research data and the research data will be saved in a password protected file.

The research data will be retained in a secured storage facility for a minimum of 7 years after completion of research study or date of publication of the research using the research data, whichever is later. These documents will be retained by the Principal Investigator in a secure storage facility, accessible for inspection and copying by authorized authorities.

## **8. SAMPLE SIZE AND STATISTICAL METHODS**

### **8.1. Determination of Sample Size**

The number of living kidney donor transplants performed at Singapore General Hospital (SGH) is low - usually between 10 to 20 kidney transplants per year. Therefore, it is unrealistic to plan for a randomized controlled study as it will take years to achieve sufficient numbers for an adequately powered study. We aim for this study to be a pilot study to determine if there is any trend in correlation between CYP3A4 genotype and dosing. If there is any trend in correlation, we can then propose to design an adequately powered and likely multi-centre study to confirm any preliminary findings from this pilot study

Thence, upon consultation with the biostatistician, it is decided that we will recruit 100 subjects who are between the ages of 21 and 75 years old and are scheduled to receive renal transplant

from a living donor and follow up at SGH between January 2016 to January 2023. The control group selected will be a historical cohort which had received tacrolimus based on weight-based dosing while the intervention group will be a prospective cohort.

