## 1. BACKGROUND AND RATIONALE

Tacrolimus (FK) remains the cornerstone of maintenance immunosuppressants after renal transplantation. However, it is characterised by narrow therapeutic index and large inter-individual variability in its pharmacokinetics, particularly in the dose required to reach target trough blood concentrations. Among several factors investigated for their possible influence on tacrolimus pharmacokinetics, polymorphisms in genes coding for biotransformation enzymes (cytochrome P450 (CYP) isoenzymes 3A4 and 3A5) have received much attention. Exposure to FK correlates with the cytochrome P450 (CYP) 3A4 and CYP3A5 which are polymorphically expressed. This is in part explained by the presence of single-nucleotide polymorphisms (SNPs) in the CYP3A5 and CYP3A4 genes.

A SNP at position 6986 of the CYP3A5 gene (rs776746; 6986A>G; designated as CYP3A5 \*3) results in a splicing defect that causes non-functional CYP3A5 protein (Birdwell KA et al, 2015). In retrospective studies, it has been demonstrated that whole-blood tacrolimus trough concentration and tacrolimus dose requirements are closely associated with CYP3A5 polymorphism: patients carrying at least one CYP3A5\*1 allele have a lower tacrolimus concentration/dose ratio than that in nonexpressers (CYP3A5\*3/\*3) among kidney, liver, lung, and heart transplant recipients. In a cohort of kidney transplant recipients, a 2.3-fold difference was observed in the daily dose required to maintain target FK trough concentration in CYP3A5\*3\*3 and CYP3A5\*1\*1 patients (Haufroid V et al, 2004). Moreover, a significant delay in reaching target FK trough concentration and a shorter time to acute rejection were observed during the first 2 weeks after kidney transplantation in CYP3A5 expressers (MacPhee et al, 2004).

To date, renal transplant (RTx) recipients receive standard weight-based dosing of FK and therapeutic drug monitoring is employed for subsequent dose adjustment to ensure target FK concentration is attained. However, the current weight-based dosing strategies to guide the initial FK dosing have been poorly predictive of the actual FK dose required to attain therapeutic FK level (Loh PT et al, 2008). With the increased possibility of sub-therapeutic FK level during the early phase post renal transplantation, it puts them at a higher risk of developing acute rejection.

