## **2. HYPOTHESIS AND OBJECTIVES**

We hypothesise that the adaptation of CYP3A5 genotype-based FK dosing will lead to earlier FK target achievement and consequently, better clinical outcome after RTx.

This study aims to shed light on the possible impact of CYP3A genotype-based FK dosing on FK target achievement and clinical outcome after RTx in a multi-ethnic population where current evidence is lacking. This data would be helpful to the physicians so that by knowing the genotype of the patient before undergoing transplantation, they would be able to decide on the starting dose of FK so as to avoid low trough levels and risk of acute rejection or high trough levels and risk of nephrotoxicity.

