## **4. STUDY POPULATION**

### **4.1. List the number and nature of subjects to be enrolled.**

The number of living kidney donor transplants performed at Singapore General Hospital (SGH) is low - usually between 20 to 30 kidney transplants per year. Therefore, it is unrealistic to plan for a randomized controlled study as it will take years to achieve sufficient numbers for an adequately powered study. We aim for this study to be a pilot study to determine if there is any trend in correlation between CYP3A4 genotype and dosing. If there is any trend in correlation, we can then propose to design an adequately powered and likely multi-centre study to confirm any preliminary findings from this pilot study.

Thence it is decided that we will aim to recruit 100 subjects who are between the ages of 21 and 75 years old and are scheduled to receive renal transplant from a living donor and follow up at SGH between January 2021 to January 2023. The control group selected will be a historical cohort which had received tacrolimus based on weight-based dosing while the intervention group will be a prospective cohort.

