#### Treatment/dosing:

The standard arm will comprise of historical controls who are patients who had received renal transplant from a living donor and followed up at SGH between January 2016 - December 2020 and received standard weight-based dosing of tacrolimus.

The intervention genotyping arm will comprise of patients who are scheduled to receive renal transplant from a living donor between January 2021 to January 2023. They will be assigned to receive the initial CYP3A5 genotype-based tacrolimus (FK) dose as determined by their CYP3A5 genotype:

| Likely phenotype                               | Diploypes | Initial Prograf ® dosing
(mg/kg/day given in 2 divided doses) |
|--|-----------|---|
| Extensive metabolizer
(CYP3A5 expresser)    | CYP3A*1*1 | 0.20  |
| Intermediate metabolizer
(CYP3A5 expresser) | CYP3A*1*3 |   |
| Poor metabolizer
(CYP3A5 non-expresser)     | CYP3A*3*3 | 0.15  |

The FK dose will be rounded off to the nearest 0.5 mg. FK will be administered at 8 am and 8 pm on an empty stomach.

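### The pilot's stated signal for a larger study is a genotype–dosing correlation, which the design itself creates in early doses and which does not test earlier target attainment

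*Protocol*

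**What the plan says.** Sections 4.1 and 8.1 of the protocol carry the same rationale. Living-donor numbers are low, no randomised trial is planned, and 8.1 then states: "We aim for this study to be a pilot study to determine if there is any trend in correlation between CYP3A4 genotype and dosing". Both sections continue: "If there is any trend in correlation, we can then propose to design an adequately powered and likely multi-centre study". Neither gives a threshold, and neither mentions target attainment.

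The rest of the protocol is about something else:

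- Section 2: "We hypothesise that the adaptation of CYP3A5 genotype-based FK dosing will lead to earlier FK target achievement".
- Section 5, Endpoints: the primary endpoint is the proportion of patients in the desired trough range at first steady state, exemplified as "morning of day 3 after five unaltered FK doses", and the proportion in range on day 7.
- Section 8.2: a chi-square test compares the two dosing groups on day-3 attainment.

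On genotype and dose:

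- Section 5, FK measurement and genotyping: all participants are typed, for CYP3A5 rs776746 only.
- Section 5, Treatment/dosing, on the prospective group: "They will be assigned to receive the initial CYP3A5 genotype-based tacrolimus (FK) dose as determined by their CYP3A5 genotype". The doses are 0.20 mg/kg/day for expressers and 0.15 for non-expressers. The centre's standard starting dose is 0.15 mg/kg/day.
- Section 1 reports from retrospective studies that "whole-blood tacrolimus trough concentration and tacrolimus dose requirements are closely associated with CYP3A5 polymorphism".

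Section 8.2 also plans a mixed between-within analysis of variance, introduced with "To estimate the overall effect of CYP3A5 genotype on the outcome variables of FK daily dose, FK trough concentration and dose-adjusted FK level". The next sentence reads: "This analysis will also be used to estimate the overall effect of dosing approach on renal function". Dosing approach is named there for renal function only.

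**The concern.** A pilot's signal should be able to fail when the idea under test is wrong. This one is poorly placed to do so.

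- As written, it names a gene that the study does not type.
- Read as CYP3A5, it is satisfied in the prospective group's early doses by assignment.
- For later, titrated doses it would repeat an association that Section 1 already treats as shown.

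In neither case does it show whether choosing the starting dose by genotype brings patients into range sooner. The comparison that would show this is already planned in 8.2, but it is not the one named as grounds for a larger study.

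Section 8.2 has a related weakness. Genotype sets the early dose in one group and not in the other. An effect of genotype on dose or trough, averaged over both groups without dosing group in the model, therefore mixes biology with dosing policy and changes with the group split.

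**Working it through.** The sample size of 100 cannot be reproduced, because 8.1 gives no effect size, rates, power or group split. The check is therefore what correlation the dose rule produces on its own.

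**Inputs from the protocol**
- Expresser share p = 0.51 (Section 1).
- Starting dose in the genotype group: 0.20 or 0.15 mg/kg/day, ratio 0.20/0.15 = 1.333 (Section 5).
- Standard starting dose 0.15 mg/kg/day (Section 5).
- Dose-adjusted trough 1.8–2.5 times higher in non-expressers during the first year (Section 1).

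**Assumptions**
- 100 is the total over both groups. Section 4.1 ties the figure to 2021–2023 and 8.1 to 2016–2023.
- The genotype-group share s is 0.2–0.5. A constant transplant rate over the two windows (60 and about 24 months) gives 24/84 = 0.286 to 25/85 = 0.294, about 0.29.
- All controls stay at 0.15 mg/kg/day to the day-3 trough.

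**Correlation on day 3, in mg/kg**

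Let G = 1 for expressers and A = 1 for the genotype group, independent of each other. Dose is D = 0.15 + 0.05·G·A. Then

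corr(G, D) = ps(1−p) / √[ps(1−ps)·p(1−p)] = √[s(1−p)/(1−sp)].

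- s = 0.2: √(0.098/0.898) = 0.330
- s = 0.29: √(0.1421/0.8521) = 0.408
- s = 0.5: √(0.245/0.745) = 0.573

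At N = 100, t = r√[98/(1−r²)] is about 3.5 at s = 0.2 and 6.9 at s = 0.5. Within the genotype group alone the correlation is 1 before rounding; in controls, under the assumption, it is 0.

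**Pooled dose ratio, expressers to non-expressers** (geometric) = 1.333^s: 1.06 at s = 0.2, 1.09 at 0.29, 1.15 at 0.5.

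**How far this weakens**

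Simulation with N = 100, assumed weights of 40–100 kg and rounding to 0.5 mg gives, for s from 0.2 to 0.5:
- in mg/kg, mean r = 0.32–0.56;
- in mg, mean r = 0.12–0.27, with p < 0.05 in 21–80% of runs;
- with control doses varying by 20% (SD on the log scale), p < 0.05 in 35–100% of runs in mg/kg and 15–69% in mg.

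The figures in mg depend on the weight distribution. With mean weight 62 kg and SD 12 kg, p < 0.05 occurs in 58% of runs at s = 0.3 and 95% at s = 0.5.

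All of this concerns day 3, one of six dose time points in Section 5, Endpoints. From then on clinicians may change the dose.

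**Early trough**

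If the 1.8–2.5-fold difference held on day 3 with linear kinetics (both assumed), the expresser to non-expresser trough ratio would be 1/1.8 to 1/2.5 = 0.56 to 0.40 in controls. In the genotype group it would be 1.333/1.8 to 1.333/2.5 = 0.74 to 0.53. Pooling shrinks the log-scale genotype effect by s·ln(1.333)/ln(fold): 0.2 × 0.314 = 0.063 at the least, 0.5 × 0.489 = 0.245 at the most, or about 6–24%.

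**The case against.** Much of the case on the other side stands.

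- **Status of the wording.** Sections 4.1 and 8.1 explain why no powered trial is attempted. A reader might infer a formal go/no-go rule that the study is bound to pass. The text does not support that: it is permissive, sets no threshold or test, and speaks of confirming preliminary findings in general.
- **The operative plan is coherent.** Hypothesis, primary endpoint and chi-square test all concern target attainment. A reader might infer that the main comparison is circular. It is not: attainment is a measured trough outcome compared between dosing groups.
- **Scope of the imposed correlation.** A reader might infer that any genotype–dose association found would be an artefact. The documents do not support this. Titrated doses and dose-adjusted levels remain informative about genotype. Section 1 reports a 2.3-fold dose difference between the extreme genotypes, well above the 1.06–1.15 that assignment produces in the pooled early dose.
- **Section 8.2.** Not naming dosing group does not exclude it, and a statistical analysis plan may list the factors. The Mann-Whitney tests planned in 8.2 can cover between-group comparisons of dose and level, and dose-adjusted level is already included. This limb is supporting only.

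One thing is not answered. On any reasonable reading of dosing, the named signal can appear without the hypothesis being true: early dose is assigned, and later dose requirement is already reported as linked to genotype.

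**Conclusion.** The point holds as a mismatch between the stated pilot signal and the study's own hypothesis and primary endpoint, together with a probable gene-name slip. Under the stated assumptions (total of 100, 20–50% in the genotype group, controls constant at 0.15 mg/kg/day) and the protocol's 51% expressers, the design alone gives a pooled correlation of about 0.33–0.57 with day-3 dose in mg/kg. That range is an upper case: the correlation falls when dose is expressed in mg or control doses vary, and the argument does not extend to titrated doses.

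Importance is minor to moderate. The planned day-3 chi-square test is unaffected. What suffers is the basis on which the pilot says it would recommend a larger study and, secondarily, the interpretation of a pooled genotype effect on early dose and trough.

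**What to change.** 1. In 4.1 and 8.1, change CYP3A4 to CYP3A5. State the pilot signal as the between-group difference in the primary endpoint, target attainment at day 3 (as tested in 8.2) and at day 7, each with a 95% CI. The same target range has to apply to both groups. Section 5, Endpoints, states one for the genotyping arm only, and that must be reconciled first.
2. In 8.2, for daily dose and trough, include dosing group and a group-by-genotype term, or report the genotype effects by group. Use the already planned dose-adjusted level as the pooled genotype outcome.

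The cost is wording and model terms; data, method family and software stay the same. The downside is precision. Group-specific standard errors are about 1/√0.5 = 1.4 times the pooled one at an equal split. With 20% in the genotype group they are 1/√0.2 = 2.2 times there and 1/√0.8 = 1.1 times in controls, so an interaction estimate would be rough.

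For the attainment difference, with assumed rates of 30–50%, the 95% CI half-width runs from 1.96·√[0.3·0.7·(1/50+1/50)] = 0.18 to 1.96·√[0.25·(1/20+1/80)] = 0.245. That is about 18 to 25 percentage points: usable for a pilot signal, not for confirmation.
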